23.2.2 Sub-study

For the countries in the sub-study, a smaller effect size is expected compared to the main study. Thus, a smaller variation (standard deviation) is expected for the mean change in CDAI from baseline. For a sample size of 15 subjects and a standard deviation for the mean change of 2.5 points, a 95% confidence interval will be around 3.2 points wide with 80% probability. This interval width provides an acceptable precision of the estimate of the primary efficacy endpoint.

The sub-study is designed to provide a minimum of 15 subjects in each of the treatment groups (Part 2 only).

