23.2 Determination of Sample Size

Calculations of sample size are based on a 95% confidence interval for the mean change in CDAI from baseline.

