23.2.1 Main study

For a sample size of 25 subjects, and a standard deviation for the mean change of 3 points, a 95% confidence interval will be around 2.8 points wide with 80% probability. This interval width provides a good precision of the estimate of the primary efficacy endpoint. For a sample size of 30 subjects, the interval will be around 2.5 points wide, which provides even better precision. If the sample size is larger, or if the standard deviation is smaller, the interval will be shorter (i.e., the precision will be higher). A larger standard deviation than 3 points is unlikely. SAS proc power is used for the calculations.

The study is designed to provide a minimum of 30 subjects in each of the treatment groups that proceed to Part 2, and a total of 90 patients.

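### Sub-study precision of 3.2 points rests on an SD lowered to 2.5 without support; on the main-study SD of 3 the width is about 3.8 points

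*Protocol*

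**What the plan says.** Protocol 23.2 sets the basis for both parts of the trial: "Calculations of sample size are based on a 95% confidence interval for the mean change in CDAI from baseline".

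- **Main study (Protocol 23.2.1).** The starting point is "For a sample size of 25 subjects, and a standard deviation for the mean change of 3 points", giving a width of about 2.8 points with 80% probability. With 30 subjects the width is about 2.5. An SD above 3 is called unlikely, and SAS proc power is named as the tool.
- **Sub-study (Protocol 23.2.2).** The section opens with "For the countries in the sub-study, a smaller effect size is expected compared to the main study". The next sentence is "Thus, a smaller variation (standard deviation) is expected for the mean change in CDAI from baseline". The calculation then takes n = 15 and SD 2.5, and its stated result is "a 95% confidence interval will be around 3.2 points wide with 80% probability". That width is called acceptable, and the sub-study is sized at no fewer than 15 subjects in each treatment group.

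Neither the protocol nor the SAP gives any other reason for 2.5.

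**The concern.** The mean change and the between-patient SD of the change are separate parameters. A lower mean leads to a lower SD only under a further assumption, for example that spread scales with response, and none is stated. The SD is also applied to every treatment group, placebo included. If the smaller effect means a smaller effect of AP1189 over placebo, it has no bearing on the spread among placebo patients.

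The interval width is the only justification given for 15 per group. Protocol 15.2 has the sub-study analysed separately as well as pooled, and SAP 3.5 asks whether the effect in these two countries is comparable with that in the main study. Readers will therefore rely on the sub-study's stand-alone precision, and the stated figure benefits from a reduction in SD that has not been justified.

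**Working it through.** **Inputs.** From Protocol 23.2 to 23.2.2: confidence level 95%; probability 80%; main study n = 25 and 30 with SD 3; sub-study n = 15 with SD 2.5.

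**Formula.** Full width of a one-sample t-interval that is attained with 80% probability:

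W = 2 × t(0.975, n−1) × SD/√n × √[χ²(0.80, n−1)/(n−1)]

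**Step 1: reproduce the plan's figures.**

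| n | SD | t | χ²(0.80) | √[χ²/(n−1)] | W | Stated |
|---|---|---|---|---|---|---|
| 25 | 3 | 2.064 | 29.55 | 1.110 | 2.75 | 2.8 |
| 30 | 3 | 2.045 | 35.14 | 1.101 | 2.47 | 2.5 |
| 15 | 2.5 | 2.145 | 18.15 | 1.139 | 3.15 | 3.2 |

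For the last row: 2 × 2.145 × 2.5/3.873 × 1.139 = 3.15. The variant conditional on the interval covering the true mean gives 2.76, 2.47 and 3.17, so either form matches after rounding. For n = 15 and SD 2.5, a plain t-width (2.77) or z-width (2.53) does not give 3.2. The 80%-probability method is therefore the one used, and the calculation is correct for its input.

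**Step 2: change only the SD, to the main-study value.** For n = 15 and SD 3:

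W = 2 × 2.145 × 3/3.873 × 1.139 = 3.78 (conditional variant 3.80), about 3.8 points.

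The width is proportional to the SD, so the ratio is 3/2.5 = 1.2, or 20% wider.

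**Step 3: chance of still reaching 3.2 points.** A width of 3.2 or less needs a sample SD of at most 1.6 × 3.873/2.145 = 2.89. With a true SD of 3 this is P[χ²(14) ≤ 14 × (2.89/3)²] = P[χ²(14) ≤ 12.99] = 0.47 (conditional variant 0.46). With a true SD of 2.5 it is 0.82.

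**Step 4: sample size equivalent.** Holding 3.2 points at 80% probability with SD 3 takes about 20 per group (W = 3.15; n = 19 gives 3.25).

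**Step 5: illustrative range.** The following SDs are assumptions and do not come from the documents. For n = 15, SD 5 gives 6.3 points and SD 7.5 gives 9.5 points.

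**The case against.** **The calculation is right.** This stands. The plan's 3.2 follows from SD 2.5, so a reader who infers a computing error would be mistaken.

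**Mean and spread can move together.** If patients are a mix of responders (proportion p, extra response d) and non-responders, the variance of the change contains p(1−p)d², which falls as d falls. The protocol says only that a smaller SD is expected, not that it must follow. This stands in part: such a model could justify a lower SD, but the protocol neither states one nor shows that it leads to 2.5. The documents therefore leave 2.5 unsupported. They do not show it to be false.

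**The sub-study patients may differ.** It is tempting to argue that population and eligibility are the same, so the SD must be the same. The documents do not support that. Exclusion criteria 17 to 20 in Protocol 16.3 apply only in Norway, and SAP 3.5 treats comparability as a question to be examined. Only the instrument and the week-4 time point are clearly common.

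**SD 3 has no source either.** Correct. The 3.8 is a like-for-like comparison with the main study, neither a best estimate nor an upper bound.

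**Little depends on it.** Efficacy analysis is descriptive (Protocol 23.5), with no test or decision rule tied to the width, and no threshold for acceptable precision is given. A reader might infer that 15 per group is too few. Without a threshold, nothing shows that 3.8 fails where 3.2 passes. What remains is a stated precision figure, the sole basis for the sample size, resting on an inference that is not supported.

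**Conclusion.** The point holds as a faulty assumption. Lowering the SD from 3 to 2.5 because a smaller effect is expected is not a valid step without an added assumption, and no data replace it. On the main-study SD, 15 per group gives a width of about 3.8 points at 80% probability, 20% more than the 3.15 behind the stated 3.2, with about a 47% chance of a width of 3.2 or less. This rests on the protocol's own method and on taking SD 3 as the comparator, itself unsourced. The effect is on the stated precision; it does not bias any planned estimate.

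**What to change.** In Protocol 23.2.2, delete the sentence that derives a smaller SD from a smaller effect. Keep 15 per group and restate the width as about 3.8 points at 80% probability, described as a like-for-like figure on the main-study SD.

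Preferably, base the width on the SD of the week-4 CDAI change in Part 1, pooled without regard to treatment. SAP 3.7 says the Part 1 interim has been performed, so the data exist, and a pooled SD needs no treatment codes and keeps the blind. Two cautions belong with it: Part 1 was planned for a minimum of 24 completers, none from Bulgaria or Moldova, and pooling over treatment includes any difference between group means. If widths for larger SDs such as 5 or 7.5 are shown, label them as illustrative assumptions.

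The cost is a less favourable stated precision. No patients are added, and conduct and analysis do not change.

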23.3 Study Participant Characteristics

The following demographic parameters will be analyzed by descriptive statistics:

Demographic characteristics (including age, weight, and height)

Protocol Code Number: SynAct-CS002

Medical history

23.4 Safety Analysis

The primary safety endpoint is the safety of AP1189 against placebo by evaluating adverse events (AEs), serious adverse events (SAEs), and laboratory abnormalities. All safety parameters (ECG, vital signs, AEs/SAEs, laboratory abnormalities, etc.) will be summarized by treatment and time point.

23.5 Efficacy Analysis

All efficacy endpoints will be evaluated by treatment group using descriptive statistics. Confidence intervals will be presented where appropriate.

23.5.1 Analysis of Primary Efficacy Endpoints

The change in CDAI after 4 weeks of treatment compared to baseline will be evaluated by assessing the following descriptive statistics by treatment group:

- Mean change in CDAI from baseline to week 4 (with confidence interval for the mean change)
- Proportion of subjects with a change in CDAI score from severe (CDAI > 22) to moderate (CDAI ≤ 22) at week 4 compared to baseline (with Clopper-Pearson confidence interval for the proportion)

23.5.2 Analysis of Secondary Efficacy Endpoints

The effects of AP1189 against placebo will be evaluated by descriptive statistics, assessing the following by treatment group:

- Proportion of subjects achieving a reduction of more than 10 (ten) swollen and/or tender joints (SJC and TJC, summarized) at week 4 compared to baseline
- Proportion of subjects achieving a change in CDAI score after 4 weeks of treatment compared to baseline
 - o Proportion of subjects with a 5-point decrease
 - o Proportion of subjects with a 10-point decrease
 - Proportion of subjects with a 15-point decrease
- Proportion of subjects achieving a change in DAS28 from DAS28 > 3.2 to DAS28 ≤ 3.2 at week 4 compared
 to baseline
- Change of HAQ-DI at week 4 compared to baseline
- Change of FACIT-Fatigue at week 4 compared to baseline
- Proportion of subjects achieving ACR response assessed by ACR 20, ACR 50, and AC70

23.5.3 Analysis of Tertiary Efficacy Endpoints

The effect of AP1189 compared to placebo will be further evaluated by descriptive statistics, assessing the following by treatment group:

- CXCL13, IL-1β, IL-6, IL-10, and TNF-α at week 4 compared to baseline
- Synovial biopsy at baseline and after 4 weeks treatment (only Part 2 at selected sites)

Protocol Code Number: SynAct-CS002

23.5.4 Analysis of other Endpoints (if applicable)

The following efficacy parameters will be summarized by treatment and time point, using descriptive statistics:

- Investigator Global VAS
- Patient Pain VAS
- CRP

23.6 Pharmacokinetic Analyses

Descriptive statistics will be used for an exploratory description of exposure in relation to effect. Plasma concentrations will be used to measure exposure.

23.7 Interim Analyses

An independent external statistician will conduct the interim analysis.

All safety parameters (ECG, vital signs, AEs/SAEs, laboratory abnormalities, etc.) and efficacy data for the primary efficacy endpoint will be summarized by treatment and time point for the subjects included in Part 1 of the study. The choice of design for Part 2 will be based on the results from the interim analysis.

The independent external statistician will ensure that the interim analyses are a completely confidential process, investigators and other study personnel will be kept blind and will only be informed about the decision of design choice for Part 2 of the study.

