15.3 Part 1 (main study only)

Following a successful screening evaluation, subjects who fulfill the enrollment criteria will be randomized in a 2:1 ratio in group A and B. One group will receive active treatment, and the other group will receive a placebo. Before randomization into group C/D (the same 2:1 ratio between active and placebo), the SC will look at blinded safety data from group A/B.

- Group A (min. 8 subjects): AP1189 dose 50 mg, once daily for 4 weeks (28 days) plus MTX (10-25 mg) weekly
- Group B (min. 4 subjects): placebo for 4 weeks (28 days) plus MTX (10-25 mg) weekly

SC Meeting

- Group C (min. 8 subjects): AP1189 dose 100 mg, once daily for 4 weeks (28 days) plus MTX (10-25 mg) weekly
- Group D (min. 4 subjects): placebo for 4 weeks (28 days) plus MTX (10-25 mg) weekly

Protocol Code Number: SynAct-CS002

15.3.1 Number of Subjects in Part 1

A minimum of 24 subjects is expected to complete Part 1 of the study. About 32 subjects are planned to be enrolled in accounting for discontinuation rate.

The rationale for the number of subjects required is outlined in the section on sample size determination.

15.4 Part 2

All subjects will be randomized into one design only, either design 1, 2, or 3 based on data from the interim analysis:

- Design 1: AP1189 dose 50 mg (min. 44 subjects) or placebo (min. 22 subjects), once daily for 4 weeks (28 days) plus MTX (10-25 mg) weekly
- Design 2: AP1189 dose 100 mg (min. 44 subjects) or placebo (min. 22 subjects), once daily for 4 weeks (28 days) plus MTX (10-25 mg) weekly
- Design 3: Continue with the same doses as in Part 1, in a 1:1:1 ratio (AP1189 50 mg (min. 22 subjects), AP1189 100 mg (min. 22 subjects) or placebo (min. 22 subjects)) plus MTX (10-25 mg) weekly

Following a successful screening evaluation, subjects who fulfill the enrollment criteria will be randomized accordingly.

15.4.1 Number of Subjects in Part 2

A minimum of 66 subjects in the main study is expected to complete Part 2 of the study, and 45 subjects in the sub-study. About 88 subjects are planned to be enrolled in the main study in accounting for discontinuation rate, and about 60 subjects in the sub-study.

The rationale for the number of subjects required is outlined in the section on sample size determination.

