15.9 Data Monitoring Committee (DMC)

The DMC is established by the sponsor and consists of a group of three study independent members: two independent external experts (a rheumatologist and a professor and specialist in hepatology and clinical pharmacology at Bispebjerg hospital), and an independent external statistician. A specific DMC charter will be developed to define roles and responsibilities.

The DMC will review the unblinded data from the interim analysis of the first min. 24 subjects from Part 1. The DMC will recommend a study design for Part 2 to the SC based on these data. All recommendations will be documented and signed by the DMC members, and they will provide a summary of the safety and tolerability data obtained in Part 1 and their design recommendation for Part 2.

The independent external statistician will analyze data for the interim analysis, following the procedure described in the statistical analysis plan and the protocol. The DMC will hereafter meet ad hoc as appropriate.

15.10 Criteria for Choice of Design for Part 2

The criteria for the choice of design 1, 2, or 3 for Part 2 are:

Design 1: AP1189 dose 50 mg (min. 44 subjects) or placebo (min. 22 subjects) plus MTX (10-25 mg) will be applied if:

- The efficacy, evaluated on the number of subjects showing reduced clinical score as defined in the protocol, is higher in the 50 mg group than in the 100 mg group.
- The safety profile of group A and B (50 mg AP1189 or placebo) is superior to the safety profile of group C and D (100 mg AP1189 or placebo).
 - The safety evaluation will focus on the number and the severity of the reported AEs and SAEs, on any laboratory findings with particular emphasis on liver and thyroid gland parameters, as well as vital signs.

Design 2: AP1189 dose 100 mg (min. 44 subjects) or placebo (min. 22 subjects) plus MTX (10-25 mg) will be applied if:

- The efficacy, evaluated on the number of subjects showing reduced clinical score as defined in the protocol, is higher in the 100 mg group than in the 50 mg group.
- The safety profile of group C and D (100 mg AP1189 or placebo) is superior or comparable to the safety profile of group A and B (50 mg AP1189 or placebo).
 - The safety evaluation will focus on the number and the severity of the reported AEs and SAEs, on any laboratory findings with particular emphasis on liver and thyroid gland parameters, as well as vital signs.

Protocol Code Number: SynAct-CS002

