Design 3: Continue with the same doses as in Part 1, in a 1:1:1 ratio (AP1189 50 mg (min. 22 subjects), AP1189 100 mg (min. 22 subjects) or placebo (min. 22 subjects)) plus MTX (10-25 mg) will be applied if:

- The evaluation shows comparable safety profiles and comparable efficacy, evaluated on the number of subjects showing reduced clinical score as defined in the protocol, in the 50 and 100 mg groups.
- The safety evaluation will focus on the number and the severity of the reported AE and SAE, on any laboratory findings with particular emphasis on liver and thyroid gland parameters, as well as vital signs.

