### **3.2** Analysis Data Sets

The sets of subjects to be analyzed are defined as follows:

- The safety analysis set consists of all subjects who received the study medication at least once, analyzed by received treatment.
- The **pharmacokinetic (PK) analysis set** consists of all subjects who completed the study and did not have any protocol deviation or events implying a bias for the PK evaluation.
- The efficacy analysis set consists of all randomized subjects who received the study medication at least once, analyzed by randomized treatment (intention to treat). A second analysis of the primary efficacy endpoint, for robustness, will be performed for all randomized subjects who complete the study without any major protocol violations (per protocol).

All safety and tolerability analyses will be conducted on the safety data set, all PK analyses will be conducted on the pharmacokinetic data set, and all efficacy analyses will be conducted on the efficacy data set.

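### For the main study, Part 1 efficacy results help choose the Part 2 design and are then pooled into the final by-dose estimates, with no main-study Part 2-only summary or caveat in the supplied SAP text

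*Protocol*

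**What the plan says.** **The interim chooses the design.** Protocol 23.7: "The choice of design for Part 2 will be based on the results from the interim analysis". Protocol 15.10 gives the criteria. Design 1 (50 mg only) has this efficacy criterion, with 100 mg as the comparator: "The efficacy, evaluated on the number of subjects showing reduced clinical score as defined in the protocol, is higher in the 50 mg group". Design 2 mirrors this for 100 mg. Design 3 keeps both doses if "The evaluation shows comparable safety profiles and comparable efficacy" on the same count. Each design also has a safety criterion. No numerical margin defines comparable. SAP 3.7 confirms that the CDAI results, including the shift to CDAI ≤ 22, were tabulated by treatment for Part 1 and reviewed unblinded by the DMC.

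**The same subjects count at the end.** Protocol 23.2.1: "The study is designed to provide a minimum of 30 subjects in each of the treatment groups that proceed to Part 2", with 90 in total. SAP 3.2 defines an efficacy set that "consists of all randomized subjects who received the study medication at least once, analyzed by randomized treatment (intention to treat"), without a split by Part.

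**What is reported separately.** The main study, the sub-study and all data pooled (Protocol 15.2, SAP 3.5); country and site (SAP 3.8); rescue use (SAP 6.1). None of these isolates Part 2 within the main study. SAP 3.9 states that the study has no multiplicity issues. SAP 3.7 asks for discrepancies between interim and final data to be documented, but does not mention selection.

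**The concern.** Data that helped make a choice are biased once that choice is taken as given. If one dose goes forward because it had more responders, its Part 1 rate is on average too high. If both go forward because their counts were close, the Part 1 difference is on average too near zero. Pooling with Part 2 dilutes this but does not remove it, and adjusting for baseline or cohort does not help.

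The trial's whole efficacy output is descriptive estimates by treatment group, and readers will use them to compare doses for the next trial. In the supplied text, those readers are neither told that the pooled figures contain the selecting data nor shown the main-study figures without them.

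**Working it through.** **Inputs.** Protocol 15.3: at least 8 per active dose in Part 1, and 4 + 4 placebo. Protocol 15.4: 44 active and 22 placebo (Designs 1/2), or 22/22/22 (Design 3). Protocol 23.2.1: SD 3 points. True response rates and the margin for comparable are not in the documents. I assume them and show ranges.

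**Does the final count include Part 1?** No sentence says so outright, but the numbers require it.
- Design 3: 8 + 22 = 30 per group.
- Designs 1/2: 8 + 44 = 52 on the kept dose, 8 + 22 = 30 placebo, 8 on the dropped dose, total 90.
- Overall: 24 + 66 = 90.

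**The plan's own precision figures.** Width = 2 · t(0.975, n−1) · (SD/√n) · √[χ²(0.80, n−1)/(n−1)].
- n = 25: 2 × 2.064 × 0.600 × √(29.55/24) = 2.75 (stated: about 2.8).
- n = 30: 2 × 2.045 × 0.548 × √(35.14/29) = 2.47 (stated: about 2.5).

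Both reproduce.

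**Designs 1/2, responder proportion.** Exact binomial enumeration, 8 per dose, both true rates 40%. A dose is picked if the counts differ by more than h. Pooled bias = (expected Part 1 rate of the picked dose − 40%) × 8/52. SE = √(0.4 × 0.6/52) = 6.8 points.

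| h | Part 1 rate of picked dose | Pooled bias | Bias/SE |
|---|---|---|---|
| 0 | 52.2% | 12.2 × 8/52 = 1.9 points | 0.28 |
| 1 | 57.3% | 17.3 × 8/52 = 2.7 points | 0.39 |
| 2 | 63.2% | 23.2 × 8/52 = 3.6 points | 0.52 |

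Over true rates of 20% to 50% the bias runs from 1.7 to 4.1 points, with SE 5.6 to 6.9. The largest value needs a 20% true rate and h = 2, when a single dose is picked only about 11% of the time.

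**Designs 1/2, mean CDAI change.** Equal doses, better one always taken, SD 3. Part 1 bias = SD/√(π × 8) = 0.60 points. Pooled: 0.60 × 8/52 = 0.09 points, against SE 3/√52 = 0.416, so 0.22 SE. In simulation, two-sided 95% coverage stays about 95%, but misses in the favourable direction rise from 2.5% to 3.7%. The ratio to the SE stays about 0.22 if the SD is 6, 10 or 12.

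**Design 3, dose difference.** True rates 30% and 50%; both kept if the counts differ by at most h. Pooled difference = (8 × Part 1 difference + 22 × 20)/30. SE = √[(0.21 + 0.25)/30] = 12.4 points.

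| h | Chance of Design 3 | Part 1 difference | Pooled difference | Shrinkage/SE |
|---|---|---|---|---|
| 0 | 0.14 | 0.0 | 14.7 points | 0.43 |
| 1 | 0.42 | 3.3 | 15.5 points | 0.36 |
| 2 | 0.66 | 8.4 | 16.9 points | 0.25 |

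With equal true rates the difference is unbiased, and each dose's own rate is off by no more than about 0.5 points.

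**What a Part 2-only estimate costs.**
- Width at SD 3, Design 3: 2.97 (n = 22) v 2.47 (n = 30), ratio 1.20.
- Width at SD 3, Designs 1/2: 1.98 (n = 44) v 1.80 (n = 52).
- Root-mean-square error, Design 3, 30% v 50%, h = 1: pooled 11.8 points v Part 2-only √(0.46/22) = 14.5.
- Root-mean-square error, Designs 1/2 at 40%: pooled 6.9 v 7.4 points with h = 0, and level at 7.4 with h = 2.

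**The case against.** Several counter-arguments stand.

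- **A Part 2-only result does exist.** A reader might infer that the plan has none. The Bulgaria/Moldova sub-study is Part 2 only, those countries were not in Part 1, and it is analysed separately. It does not replace a main-study result, since it covers other countries with at least 15 per group and Protocol 23.2.2 expects a smaller effect there.
- **A by-Part table cannot be ruled out.** Appendix 4 and the DMC charter are separate documents that were not supplied. SAP Appendix 5 shows that Appendix 4 holds output not described in the SAP body.
- **Part 2 responder counts can be recovered** by subtracting the interim tables from the final ones, apart from data corrections. That is true, but a reader of the final report should not have to do it.
- **The bias is small beside the sampling error**, and dropping Part 1 usually costs more in variance than it gains. This argues against drawing dose conclusions from Part 2 alone. It does not argue against an added table.
- **Nothing inferential is at stake.** All efficacy analysis is descriptive, with no test, alpha or power. A reader might infer an inflated false-positive claim, but the plan makes no such claim to inflate.
- **The enumeration uses efficacy alone.** The safety criteria and the Steering Committee's judgement are not modelled. If they override the responder counts, the selection is weaker than shown.

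**Conclusion.** The point holds for the main study, and the effect is modest. Part 1 responder results help choose the design, the same subjects enter the final by-dose estimates, and the supplied text offers neither a main-study Part 2-only summary nor a caveat.

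The direction depends on the design. Under Designs 1/2 the chosen dose's pooled rate is overstated by about 2 to 4 points (about 0.3 to 0.5 SE at an assumed 40% true response). Under Design 3 a true difference is understated, for example 20 points becoming about 15 to 17 (about 0.25 to 0.43 SE, assuming 30% v 50% and counts within 0 to 2). With equal doses the Design 3 difference carries no bias. All these sizes rest on assumed response rates, an assumed margin and 8 subjects per dose in Part 1.

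Two stronger readings are not supported. One is that the final dose effects are inflated whichever design was used: Design 3 pulls a true difference towards zero. The other is that Design 3 is known to be the design in use. The pooled-dose tables in SAP Appendix 5 and a sub-study of 45 = 3 × 15 suggest it, but the SAP never names the design chosen.

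**What to change.** 1. In SAP 6.1.1, add as a supplementary analysis both primary variables (mean CDAI change from baseline to week 4; proportion reaching CDAI ≤ 22) by treatment for main-study Part 2 subjects only, shown beside the pooled result.
2. In SAP 3.7, state which design was chosen and that the pooled dose-specific estimates include the data that informed that choice, so they should be read together with the Part 2-only estimates.
3. Keep the pooled analysis as the main one. If Appendix 4 already has a by-Part table, a cross-reference replaces item 1.

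The cost is two tables from data already collected and a short statement. The Part 2-only interval for the mean is about 20% wider under Design 3 (2.97 v 2.47 points at SD 3) and so misses the widths cited in Protocol 23.2.1, which is acceptable in a supplementary table.
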